3.5.3 Dose Escalation

In the Phase I, Stage I, single patient dose escalation phase of this study, each patient must have received all of their planned doses of BT1718 during the first cycle (28 day DLT period) to make a decision to escalate to the next single patient cohort. If a patient does not receive all their planned doses of BT1718 during that cycle for reasons other than toxicity, a further evaluable patient may need to be recruited before a decision can be made.

Once the dose escalation cohorts are expanded following a 3+3 design, patients must have received \geq 75% of their planned dose exposure of BT1718 during the first cycle (28 day DLT period) in order to dose escalate. If any patients in the three to six patient cohorts receive <75% of their planned doses during the first cycle (28 day DLT period) for reasons other than BT1718 related toxicity, further evaluable patients may need to be recruited before a decision can be made (see section 5.6.1).

Phase I of the trial has completed.

4 PATIENT SELECTION

4.1 Eligibility criteria

The patient must fulfil the eligibility criteria listed below:

4.1.1 Inclusion criteria

- 1. Written (signed and dated) informed consent and be capable of co-operating with treatment and follow-up
- 2. Phase I, dose escalation phase (Stages 1 and 2):
 - Histologically or cytologically proven advanced solid tumour, refractory to conventional treatment, or for which no conventional therapy is considered appropriate by the Investigator or is declined by the patient.

Phase IIa, expansion phase:

- Histologically or cytologically proven advanced solid tumour of particular interest based on pre-clinical and clinical data, refractory to conventional treatment, or for which no conventional therapy is considered appropriate by the Investigator or is declined by the patient. Phase IIa expansion cohorts will be:
 - a. Squamous NSCLC cohort retrospective MT1-MMP testing.
 - b. Basket cohort (advanced solid tumours, excluding patients eligible for one of the other recruiting expansion cohorts) high MT1-MMP expression by IHC assay using archival tumour sample (mandatory fresh tumour samples for those patients without available archival tumour samples or additional analysis is deemed necessary). Retrospective testing may be permitted for tumour types estimated to have high MT1-MMP positivity rates as per the Laboratory manual.
 - c. Additional expansion cohort(s) of squamous oesophageal cancer if confirmed as recruiting by the Sponsor (see Section 3.2).
- At least one measurable lesion according to RECIST Version 1.1, that has had objective progression on or after the last therapy

- 3. Life expectancy of at least 12 weeks
- 4. World Health Organisation (WHO) performance status of 0 1 (Appendix 1)
- 5. Haematological and biochemical indices within the ranges shown below. These measurements should be performed to confirm the patient's eligibility.

Laboratory Test	Value required
Haemoglobin (Hb)	≥90.0 g/L, or ≥100.0 g/L if transfusion within last four weeks
Absolute neutrophil count (ANC)	≥1.5 x 10 ⁹ /L
Platelet count	≥100 x 10 ⁹ /L
Bilirubin	≤1.5 x upper limit of normal (ULN) NB: >1.5 x ULN, acceptable if conjugated bilirubin is ≤1.5 x ULN

Alanine amino-transferase (ALT), aspartate amino-transferase (AST) and alkaline phosphatase (ALP)	≤2.5 x ULN (or ≤5 x ULN if has liver metastases)
Renal function	
Either:	
Serum creatinine	≤1.5 x ULN
Or:	
Calculated creatinine clearance (using the Wright or Cockcroft & Gault [C&G] formula)	GFR ≥50 mL/min (uncorrected value)
Or:	
Isotope clearance measurement *	GFR ≥50 mL/min (corrected value)

* Isotope clearance result to be used to confirm eligibility if calculated C&G/Wright method results in a glomerular filtration rate (GFR) of =50 mL/min.

- 6. 16 years or over at the time consent is given
- 7. Consent to access and analyse any available archival tissue.

4.1.2 Exclusion criteria

- 1. Radiotherapy (except for palliative reasons), systemic anti-cancer therapy (with the exception of lifelong hormone suppression such as LHRH agents in prostate cancer) or investigational medicinal products during the previous four weeks (six weeks for nitrosoureas, mitomycin-C) before treatment (or first dose of an immunotherapy during the previous 12 weeks).
- 2. Prior bone marrow transplant, myeloablative conditioning, or extensive radiotherapy to greater than 25% of bone marrow, within previous eight weeks of first BT1718 dose.
- 3. Ongoing toxic manifestations of previous treatments greater than NCI CTCAE Grade 1. Exceptions to this are alopecia, amenorrhea/oligospermia and any other ongoing toxic manifestation which in the opinion of the Investigator and the Medical Advisor should not exclude the patient.
- 4. Any central nervous system (CNS) metastases (unless had local therapy and are asymptomatic and radiologically-stable off steroids for the last four weeks).
- 5. Current or prior malignancy which could affect compliance with the protocol or interpretation of results. Patients with curatively-treated non-melanoma skin cancer, non-muscle-invasive bladder cancer, or carcinomas-in-situ are generally eligible.
- 6. Female patients who are able to become pregnant (or are already pregnant or lactating). However, those patients who have a negative serum or urine pregnancy test before enrolment and agree to use two forms of contraception (one effective form plus a barrier method) [oral, injected or implanted hormonal contraception and condom; intra-uterine device and condom; diaphragm with spermicidal gel and condom] or agree to sexual abstinence⁸, effective from the first administration of BT1718, throughout the trial and for six months afterwards are considered eligible
- 7. Male patients with partners of child-bearing potential (unless they agree to take measures not to father children by using a barrier method of contraception [condom plus spermicide] or to sexual abstinence⁹ effective from the first administration of BT1718, throughout the trial and for six months

^a Abstinence is only considered to be an acceptable method of contraception when this is in line with the preferred and usual lifestyle of the subject. Periodic abstinence (e.g., calendar, ovulation, symptothermal, post ovulation methods) and withdrawal are not acceptable methods of contraception.

⁹Abstinence is only considered to be an acceptable method of contraception when this is in line with the preferred and usual lifestyle of the subject. Periodic abstinence (e.g., calendar, ovulation, symptothermal, post-ovulation methods) and withdrawal are not acceptable methods of contraception.

afterwards. Men with partners of child-bearing potential must also be willing to ensure that their partner uses an effective method of contraception for the same duration for example, hormonal contraception, intrauterine device, diaphragm with spermicidal gel or sexual abstinence). Men with pregnant or lactating partners must be advised to use barrier method contraception (for example, condom plus spermicidal gel) to prevent exposure of the foetus or neonate.

- 8. Surgery from which the patient has not yet recovered.
- 9. At high medical risk because of non-malignant systemic disease including active uncontrolled infection.
- 10. Known to be serologically positive for hepatitis B, hepatitis C or human immunodeficiency virus (HIV).
- 11. Patients with significant cardiovascular disease are excluded as defined by:
 - a. Current congestive heart failure requiring therapy (NYHA III or IV Appendix 3) or known LVEF <40% (moderate to severe)
 - b. History of unstable angina pectoris or myocardial infarction up to six months prior to trial entry, or of current poorly controlled angina (symptoms weekly or more)
 - c. Presence of symptomatic or severe valvular heart disease (severe by local echographic criteria or AHA/ACC Stage C or D Appendix 4)
 - d. History of a clinically significant cardiac arrhythmia up to six months prior to trial entry (asymptomatic atrial fibrillation or asymptomatic first-degree heart block are permitted)
- 12. Previous known allergy to one of the constituents or excipients of BT1718.
- 13. Is a participant or plans to participate in another interventional clinical trial, whilst taking part in this Phase I/IIa study of BT1718. Participation in an observational trial or interventional clinical trial which does not involve administration of an IMP and which would not place an unacceptable burden on the patient in the opinion of the Investigator and Medical Advisor would be acceptable.
- 14. Any other condition which in the Investigator's opinion would not make the patient a good candidate for the clinical trial.

4.2 Patient enrolment

Before enrolling the patient in the trial, the Investigator or designated representative should determine the eligibility of the patient during the trial screening period.

Eligible patients must be enrolled in the electronic data capture (EDC) system by site staff and then registered at the Centre for Drug Development (CDD) before they start treatment with BT1718. Eligible patients will be allocated a study number by the EDC system during the enrolment process. The CDD will send confirmation of the patient registration including the assigned dose level to the Investigator following enrolment of the patient. Study treatment may only be administered after confirmation has been received.

5 TREATMENT

5.1 Selection of the Phase I starting dose and schedule

Therefore, the proposed starting dose for the FIH Phase I trial is 0.6 mg/m² twice weekly.

5.2 Dosing schedule/treatment schedule

5.2.1 Phase I, dose escalation phase, Stage 1, dosing schedule/treatment schedule

BT1718 will be administered intravenously twice weekly for three out of four weeks (dosing on Days 1, 4, 8, 11, 15 and 18 +/- 1 day). Each cycle of treatment will consist of 28 days, and patients may continue until disease progression, depending on the availability of BT1718 (see Section 5.6). The starting dose will be 0.6 mg/m^2 .

Phase I of the trial has completed.

5.2.2 Phase I, dose escalation phase, Stage 2, dosing schedule/treatment schedule

In addition to evaluating a twice weekly dosing schedule in Stage 1 above, a once weekly dosing schedule will also be evaluated in Stage 2. Stage 2 will open at a dose where there is expectation of potential biological activity based on available PK, toxicity and/or PD data from Stage 1.

BT1718 will be administered intravenously once weekly for three out of four weeks (dosing on Days 1, 8 and 15 +/- 1 day). Each cycle of treatment will consist of 28 days and patients may continue until disease progression, depending on the availability of BT1718. The starting dose of the once weekly regime will be up to 100% of the overall weekly dose from the last completed cohort deemed safe from the twice weekly schedule (Phase I, Stage 1). Stage 2 will include a minimum of three evaluable patients following a 3+3 design.

Alternative dosing schedules may be considered by the Sponsor based on emerging data during the study, for example if the toxicology profile is benign with the twice weekly dosing regimen, continuous bi-weekly dosing maybe evaluated. Emerging data obtained during Phase I may be used in the decision to proceed with the Phase IIa stages. In addition, depending on the patient populations selected, an increased dosing frequency may also be considered. If any changes are made to the dosing schedule a substantial amendment will be submitted to the MHRA, REC and HRA for approval.

Phase I of the trial has completed.

5.2.3 Phase IIa, expansion phase

BT1718 will be administered intravenously at the once weekly RP2D as defined by Phase I, Stage 2; refer to Section 5.2.2.

Please refer to section 3.2 for further details on the expansion cohorts.

5.3 Dose Escalation communication plan

5.3.1 Organisation and preparation for dose decision meetings

Dose decision meetings will be organised by the Sponsor for review of patient data after each patient in the single patient dose escalation cohorts has completed Cycle 1 (28 day DLT observation period). When cohorts are expanded to 3+3, dose decision meetings will be organised by the Sponsor for review of patient data once each cohort is complete.

Dose decision meetings may also be arranged during the expansion phase in response to emerging tolerability data, including a formal assessment after the first six patients.

Required attendees / functional groups are as defined in the Sponsor's SOP.

Prior to the dose decision meeting, the Sponsor will distribute the agenda and all necessary data to the meeting attendees, specifying which patients and data will form part of the review. The essential data to be reviewed to make decisions concerning changes in dose will be defined in the monitoring guidelines for the study. These will consist primarily of clinical data listings from Data Management, safety data listings from Pharmacovigilance and any available PK and **Example 1** data from the analysing laboratory(ies).

5.3.2 Areas to be discussed at dose review meetings

Areas which should be discussed at the dose review meeting include but are not limited to:

- Outline any relevant criteria specified by the protocol relating to changes in dose levels to the attendees e.g. study dose escalation scheme, DLT criteria, criteria for expansion of cohorts etc. Patients treated since the last dose review meeting including BT1718 related AEs noted and duration of treatment.
- Assessment and agreement on any DLTs that may have occurred and resulting actions.
- Relevant PK data available since the last dose decision meeting.
- Any additional relevant information relating to AEs or patient safety which may have arisen following distribution of listings for the meeting and will therefore not be documented in the listings.
- Any possible concern after the review of cumulative data e.g. toxicities.
- Assessment and agreement on the appropriate next dose level or other action such as dose expansion, dose reduction or halt to recruitment.

5.3.3 Follow-up of dose decision meetings

Following the meeting the Sponsor will prepare and disseminate minutes documenting what data was reviewed for which patients and with the outcome stated. DLTs and serious adverse events (SAEs) discussed (as defined in the protocol) will be documented fully in the minutes and listed by patient. If changes to these emerge as part of the review and discussion the minutes will reflect these and any actions to be taken as a result. Dose review meeting minutes will be distributed by the Sponsor to the CI, all study PIs and any other relevant site staff.

If due to exceptional circumstances, the CI is not able to attend the dose review meeting, the meeting minutes will be sent to the CI by email who will respond to confirm agreement as soon as possible with the dose decision prior to the recruitment of the next patient to the relevant cohort.

The outcome of the dose review will also be approved by the Sponsor's Head of Medical Sciences ahead of recruitment of the next patient to the relevant cohort. Patients can only be registered and treated on the study following email confirmation from the Sponsor to the site of the agreed dose level for the specific patient.

5.3.4 Dissemination of Safety data between dose decision meetings

Safety information relating to SAEs and DLTs will be collected and provided to the MHRA and REC as outlined in Section 9. Where the Sponsor becomes aware of significant relevant safety information (such as a DLT) during treatment of patients on the study, this will be communicated to all PIs and relevant site staff by email as soon as is reasonably possible. Updates regarding the DLT assessment and actions to be taken will also be provided by email where needed with follow-up phone-calls where required.

Phase I of the trial has completed.

5.4 Dose escalation scheme

5.4.1 Phase I, dose escalation phase, Stage 1 - (twice weekly dosing)

In Phase I, dose escalation phase, Stage 1, dose increases will initially be up to a maximum of 100% in the single patient cohorts, driven by reported safety data and any available PK data, until the first CTCAE Grade 2 toxicity considered by investigators to be at least probably related to BT1718 is observed, or until the dose exceeds 6 mg/m² twice weekly (i.e. 12mg/m² over the week). Subsequent cohorts will revert to a standard 3+3 format with dose escalation steps up to 100% driven by reported safety and available PK data. If a single DLT is seen among the initial three patients, the cohort will be expanded up to a total of six evaluable patients. The dose will be considered tolerable if less than two out of six evaluable patients experience a DLT.

In the single patient cohorts, the next patient can receive their first dose of BT1718 once the preceding patient has completed their DLT period (the first 28 days) and the Sponsor and study team has deemed it safe to proceed to the next cohort. In the 3+3 patient cohorts the first patient will be observed for toxicity for 7 days from Day 1 before subsequent patients receive their first dose of BT1718. Please refer to Section 5.3 for details of the process for dose escalation review and dissemination of information.

Patients who receive less than 75% of their planned doses during the first cycle (28 days DLT period) for reasons other than toxicity will not be evaluable for assessment of DLT for dose review decisions and may be replaced in the cohort. Reported safety information for these patients may however be considered to guide the percentage change in dose levels. In order to make the decision to escalate the BT1718 dose, the required number of evaluable patients must have completed one cycle (approximately 28 days).

Phase I of the trial has completed.

5.4.2 Phase I, dose escalation phase, Stage 2 - (once weekly dosing)

In Phase I, dose escalation phase (Stage 2) dose increases may be up to 100% of the previous dose level, and will be driven by reported safety and available PK data. If a single DLT is seen among the initial three patients, the cohort will be expanded up to a total of six evaluable patients. The dose will be considered tolerable if less than two out of six evaluable patients experience a DLT.

In the 3+3 patient cohorts the first patient will be observed for toxicity for 7 days from Day 1 before subsequent patients receive their first dose of BT1718. Please refer to Section 5.3 for details of the process for dose escalation review and dissemination of information.

Patients who receive less than 75% of their planned doses during the first cycle (28 days DLT period) for reasons other than toxicity will not be evaluable for assessment of DLT for dose review decisions and may be replaced in the cohort. Reported safety information for these patients may however be considered to guide the percentage change in dose levels. In order to make the decision to escalate the BT1718 dose, the required number of evaluable patients must have completed one cycle (approximately 28 days).

Phase I of the trial has completed.

5.4.3 Intra-patients dose escalations

No intra-patient dose escalation will be allowed.

5.4.4 Expansion of dose levels

If one instance of DLT as defined in Section 3.3 is observed in a cohort of three patients, up to six patients will be treated at that dose level. If one out of six patients experiences a DLT, dose escalation will continue. If two or more out of up to six patients experience a DLT, dose escalation will stop and this dose will be defined as non-tolerated. A maximum of six evaluable patients will be treated at a dose below the non-tolerated level to define the MTD.

The MAD will be defined as the highest dose received. This will usually represent the non-tolerated dose above the MTD, but may instead represent a maximum administrable dose if the feasible volume of infusion limits the dose before toxicity does.

If a new type of DLT or high number of DLTs/adverse events occur during the expansion phase at the RP2D, dosage reductions for patients in the expansion cohorts may be made based on ongoing tolerability monitoring and safety reporting. This will be continually monitored but also formally assessed after the first six patients have received two cycles of treatment. If a dose below the RP2D is being used and a patient is shown to tolerate that dose, their ongoing doses may be titrated up to (but not exceed) the RP2D.

Phase I of the trial has completed.

5.5 Dose modifications

5.5.1 Dose delays and reductions

Patients who experience a DLT (defined in Cycle 1 only) that resolves to Grade \leq 1 or recovers to baseline within 15 days of the start of the DLT may recommence treatment, with the agreement of the PI, Sponsor and patient. The dose should be reduced to a lower dose level. If the AE has not resolved to Grade \leq 1 or recovered to baseline within 15 days, the patient will be taken off-study. If the patient experiences a DLT at this reduced dose, either the same or different toxicity, there will be no further dose reductions and the patient will be withdrawn from the study.

Haematological toxicities

- Patients who experience a ≥Grade 3 haematological toxicity will have the subsequent doses omitted during that cycle until the toxicity resolves to <Grade 3. On resolution to <Grade 3, treatment can recommence at the same dose level during that cycle.
- If a clinically significant Grade 2 toxicity related to BT1718 (probably or highly probably) is still present when a patient is due to start the next cycle, that cycle should be delayed up to 14 days until the toxicity resolves to ≤Grade 1.
- The first time a dose is omitted or delayed, it may be given at the same dose the next time. However, if there is a subsequent need to omit or delay again, the dose should be reduced to a lower dose level (unless, in exceptional circumstances, the PI, Sponsor and patient agree that further dose omissions/delays are appropriate and provide effective control of toxicity).
- If toxicity remains clinically significant and does not recover to <Grade 2 within 15 days, the patient will be taken off-study.
- Only one dose reduction will be allowed per patient unless, in exceptional circumstances, the PI, Sponsor and patient agree that further treatment is appropriate and that a dose reduction is expected to provide effective control of toxicity.

Non-haematological toxicities:

Grade 2

- Patients who experience a clinically significant Grade 2 non-haematological toxicity related to BT1718 (probably or highly probably), that does not respond (<7 days) to supportive clinical management, will omit subsequent doses during that cycle until the toxicity resolves to <Grade 1 or baseline.
- If a clinically significant Grade 2 BT1718-related toxicity is still present when a patient is due to start the next cycle, that cycle should be delayed up to 14 days until the toxicity resolves to ≤Grade 1 or baseline.
- The first time a dose is omitted or delayed, it may be given at the same dose when recommencing. However, if there is a subsequent need to omit or delay again, the dose should be reduced to a lower dose level (unless, in exceptional circumstance, the PI, Sponsor and patient agree that further dose omissions/delays are appropriate and provide effective control of toxicity).
- If toxicity remains clinically significant and does not recover to ≤Grade 1 or baseline within 15 days, the patient will be taken off-study.

• Only one dose reduction will be allowed per patient, unless, in exceptional circumstances, the PI, Sponsor and patient agree that further treatment is appropriate and that a dose reduction is expected to provide effective control of toxicity.

Grade 3

- Patients who experience a Grade 3 non-haematological toxicity that does not rapidly respond (<3 days) to supportive clinical management, will omit subsequent doses during that cycle until the toxicity resolves to ≤Grade 1 or baseline (or non clinically significant Grade 2).
- If clinically significant ≥Grade 2 BT1718-related toxicity is still present when a patient is due to start the next cycle, that cycle should be delayed up to 14 days until the toxicity resolves to ≤Grade 1 or baseline.
- When patients recommence treatment after a Grade 3 non-haematological toxicity, the dose should be reduced to a lower dose level. If toxicity does not recover to ≤Grade 1 or baseline within 15 days, the patient will be taken off-study.
- Only one dose reduction will be allowed per patient, unless, in exceptional circumstances, the PI, Sponsor and patient agree that further treatment is appropriate and that a dose reduction is expected to provide effective control of toxicity.

Grade 4

• Patients who experience a Grade 4 non-haematological toxicity, or liver enzyme changes consistent with Hy's Law (bilirubin >2x ULN and ALT/AST >3x ULN, with no explanation other than drug), will cease further treatment and be taken off-study once accuracy of testing is confirmed.

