3.3 Definition of dose limiting toxicity

Some of the DLT and MTD definitions are derived from the NCI CTCAE Version 4.02. Please note that not all of the events described as DLTs are fully supported by NCI CTCAE but are formed by amalgams of different events in order to assist with assessments of AEs.

A DLT is defined as a probably or highly probably drug-related AE occurring during Cycle 1 (i.e. the first 28 days) which fulfils one or more of the following criteria, despite appropriate supportive clinical management (however, all clinically significant toxicities will be considered in dose review decisions and the determination of the Phase II dose):

- Neutropenia Grade 4 (absolute neutrophil count [ANC] < 0.5 x 10⁹/L) for ≥ seven days *see note;
- Febrile neutropenia with Grade 3 or 4 neutropenia ANC <1.0 x 10⁹/L and a single temperature of ≥ 38.3°C or a sustained temperature ≥38 °C for more than one hour);
- Clinically significant infection (documented clinically or microbiologically) with Grade 3 or 4 neutropenia (ANC <1.0 x 10⁹/L);
- Thrombocytopenia Grade 4:
 - a) for \geq five days *see note, or
 - b) associated with active bleeding, or
 - c) requiring platelet transfusion.
- Grade 3 or 4 toxicity to organs other than the bone marrow, EXCLUDING:
 - Grade 3 nausea;
 - $\circ~$ Grade 3 or 4 vomiting in patients who have not received optimal treatment with antiemetics; or
 - Grade 3 or 4 diarrhoea in patients who have not received optimal treatment with anti-diarrhoeals.
 - Transient, asymptomatic Grade 3 biochemical abnormalities if agreed by the Sponsor and the Study Team, including the Chief Investigator (CI).
- Fatal event;
- Any other related toxicity which leads to discontinuation of treatment in Cycle 1, or to a delay in dosing of >7 days (excluding where the delay is >7 days due to scheduling rather than a clinical decision);
- Any other related toxicity that is greater than at baseline and is judged to be a DLT by the Sponsor, including the CI and Principal Investigators (PIs).

*Note: In the event of a Grade 4 neutropenia or Grade 4 thrombocytopenia, a full blood count must be performed at least on Day 7 (neutropenia) and Day 5 (thrombocytopenia) after the onset of the event to determine if a DLT has occurred. The investigator must continue to monitor the patient closely until resolution to Grade 3 or less.

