5.7 Concomitant medication and treatment

Concomitant medication may be given as medically indicated. This includes symptomatic clinical management of BT1718 related or unrelated AEs. Vaccinations, including COVID-19 vaccines are permitted. Some vaccinations may be subject to specific Sponsor risk assessment. Details (including name and start and stop dates of the concomitant medication given) must be recorded in the patient's medical records and details entered into the electronic case report form (eCRF).

Palliative radiotherapy may be given concomitantly for the control of bone pain or other symptoms. These irradiated lesions will not be evaluable for response.

The patient must not receive other anti-cancer therapy or investigational drugs while on the trial.

As in Section 5.5 above, dosing with BT1718 may also be delayed up to 15 days if required to manage toxicity, without a patient needing to be withdrawn from study.

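### Section 5.5.1 gives conflicting stop and restart instructions for the same patient and does not say whether the DLT paragraph or the toxicity-category rules take precedence

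*Protocol*

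**What the plan says.** **Section 3.3** limits DLTs to probably or highly probably related events in Cycle 1. One criterion is "Grade 3 or 4 toxicity to organs other than the bone marrow, EXCLUDING" a short list. At Grade 4 that list removes only vomiting and diarrhoea that were not optimally treated. Grade 4 neutropenia lasting at least seven days is also a DLT.

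**Section 5.5.1** has two layers.

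- *DLT paragraph.* A DLT that reaches Grade 1 or below or "recovers to baseline within 15 days of the start of the DLT may recommence treatment", provided the principal investigator, sponsor and patient agree. On restart, "The dose should be reduced to a lower dose level". A further DLT at the reduced dose means withdrawal. The paragraph itself notes that DLTs are defined in Cycle 1 only.
- *Haematological bullets.* Grade 3 or worse holds dosing within the cycle. Once below Grade 3, dosing may resume in that cycle at an unchanged dose.
- *Non-haematological Grade 2.* Within the cycle the patient "will omit subsequent doses during that cycle until the toxicity resolves to <Grade 1 or baseline". For the next cycle, "that cycle should be delayed up to 14 days until the toxicity resolves to ≤Grade 1 or baseline".
- *Non-haematological Grade 3.* Within-cycle restart is allowed at Grade 1, at baseline, or at a Grade 2 that is not clinically significant, at a lower dose level. A patient not at Grade 1 or below or baseline by 15 days goes off-study.
- *Non-haematological Grade 4.* "Patients who experience a Grade 4 non-haematological toxicity" (or who meet Hy's Law) "will cease further treatment and be taken off-study once accuracy of testing is confirmed".

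**Section 5.7**, citing Section 5.5, says "dosing with BT1718 may also be delayed up to 15 days if required to manage toxicity".

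**The concern.** The DLT paragraph covers DLTs as a class, with no upper grade. The bullets cover toxicities by type and grade. An event can fall under both, and nothing says which layer governs. A stopping rule should not depend on which paragraph the site reads first.

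The text is still in use. Several Phase I sections nearby (5.4.1, 5.4.2, 5.6.1.1) carry a note that Phase I is complete; Section 5.5.1 does not. Section 5.4.4 expects that DLTs may occur at the recommended dose in the expansion phase.

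Patient safety is at stake first. These rules also decide who stays on treatment and at what dose. That feeds the safety profile, which is the primary expansion objective, and sometimes decides who counts as evaluable for response.

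**Working it through.** The plan gives no figure to reproduce here. The check is a comparison of the rules, followed by simple dose and day counts.

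**Step 1. The rules side by side**

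| Situation | One instruction | The other instruction |
|---|---|---|
| (a) Related Grade 4 non-haematological event in Cycle 1, not excluded by 3.3, resolved within 15 days | DLT paragraph: restart permitted, lower dose level, by agreement | Grade 4 bullet: treatment ends, patient off-study |
| (b) Haematological DLT | DLT paragraph: Grade 1 or below, or baseline; lower dose level | Haematological bullet: below Grade 3; same dose level, same cycle |
| (c) Grade 3 non-haematological event settling at a Grade 2 that is not clinically significant, above baseline | Within-cycle bullet: restart allowed | 15-day bullet: off-study |
| (d) Second DLT after a reduction | DLT paragraph: withdraw | Same paragraph: DLTs exist in Cycle 1 only |

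**Step 2. Test each row with a patient (event days are assumed, once-weekly dosing on Days 1, 8 and 15)**

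- (a) Grade 4 from Day 5, Grade 1 by Day 15. That is 15 − 5 = 10 days, within the 15-day limit, so restart is permitted. The Grade 4 bullet has no exception for resolution, so the same patient must stop.
- (b) Grade 4 neutropenia from Day 5 to Day 12 lasts 12 − 5 = 7 days, so it is a DLT. If it is Grade 2 on Day 15, the haematological bullet allows the Day 15 dose unchanged. The DLT paragraph allows no dose yet, and a lower one later.
- (c) The patient restarts properly at the residual Grade 2. If that grade persists, the 15-day bullet removes the patient. The Grade 2 off-study bullet requires the toxicity to remain clinically significant; the Grade 3 one does not.
- (d) The trigger works only if dosing resumes within Cycle 1. A DLT that begins after the Day 15 dose, or is unresolved by then, leads to restart in Cycle 2 at the earliest. Later events are then not DLTs, and the category rules apply. Those allow a further reduction in exceptional circumstances, which the DLT paragraph does not.

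**Step 3. Minor mismatches**

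- Grade 2 events: below Grade 1 within the cycle, but Grade 1 or below for the next cycle.
- Delay: the next cycle is due on Day 29. A 14-day delay runs to 29 + 14 = Day 43, and a 15-day delay to 29 + 15 = Day 44. The gap is one day.

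**Step 4. Effect on response evaluability**

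Section 3.5.1 requires one full cycle or at least 66% of planned Cycle 1 and 2 exposure, plus baseline and repeat disease assessments. There are 3 doses per cycle, so 6 in two cycles. For patient (a), dosed on Day 1 only before the event:

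- Stopped: 1/6 = 17% and no full cycle, so not evaluable.
- Restarted on Day 15 with one dose missed: up to 5/6 = 83% by dose count, so evaluable if the assessments are done. By milligrams, if the lower level is a fraction f of the first dose (not given in the protocol), exposure is (1 + 4f)/6. This reaches 66% at f = (6 × 0.66 − 1)/4 = 0.74. A complete Cycle 2 might also count as the full cycle.

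If the event comes after all three Cycle 1 doses, the full-cycle condition is met under either rule and the choice has no effect here.

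**The case against.** **On the Grade 4 conflict.** The DLT paragraph is permissive and needs sponsor agreement; the Grade 4 bullet is mandatory and more specific. A site that stops treatment breaches nothing, and no site can restart alone. This stands as far as it goes: it makes large differences between sites less likely. It does not supply precedence, because the DLT paragraph is equally specific to DLTs and has no grade limit.

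**On the restart grades.** The below-Grade-1 threshold may be a lost or mistyped sign, since the matching Grade 2 bullets read Grade 1 or below. A reader might infer that the milder event has the stricter rule. The documents do not support that firmly: the Grade 2 hold applies only to clinically significant, related toxicity that does not respond to supportive care, and restart after Grade 3 requires a lower dose level. Different thresholds for haematological and non-haematological events are also no contradiction in themselves. Row (b) stands because one event meets two rules.

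**On the delay limits.** Fourteen days for a cycle delay and fifteen for recovery can be separate limits. Only the wording in Section 5.7 conflicts, by one day, the same size as the dosing window of plus or minus one day.

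**On the second DLT.** There is no unmanaged gap after Cycle 1, because the category rules still apply. What remains is a withdrawal trigger that cannot operate where it would often be needed.

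**Conclusion.** Conflicts (a) to (d) are in the current text and should be corrected. The Grade 2 threshold and the one-day delay mismatch are minor.

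The number of patients affected is unknown. A reader might infer that every related Grade 4 non-haematological event in Cycle 1 is caught. It is not: the event must escape the Section 3.3 exclusions, resolve in time and have three-party agreement before the two rules diverge in practice.

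A reader might also infer effects on replacement. Section 5.6.1.2 does not replace patients whose exposure shortfall comes from probably or highly probably drug-related toxicity, so exposure-based replacement is unaffected. The consequence is instead that a patient lost to response evaluability on these grounds would not be replaced, in a cohort of about 16.

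Nor does missing half of the two-cycle doses settle evaluability: three doses missed in Cycle 2 gives 3/6 = 50%, but a complete Cycle 1 still qualifies. The evaluability effect is confined to cases such as the one worked above. It rests on the assumed event timing and on counting exposure by doses. An effect on adverse event rates is plausible but cannot be sized from the protocol.

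**What to change.** Reconcile Section 5.5.1 internally and with Sections 3.3 and 5.7:

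1. State which rule takes precedence when a DLT also falls under a category rule, naming Grade 4 non-haematological DLTs and haematological DLTs.
2. Align the Grade 3 within-cycle restart threshold with the 15-day off-study criterion, and say when the 15 days start.
3. Define the withdrawal trigger after a dose reduction by criteria that can apply after Cycle 1, or say that it is limited to Cycle 1.
4. Confirm the Grade 2 within-cycle threshold and make the delay limit in Section 5.7 match Section 5.5.1.

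Which clinical rule applies in each case is for the sponsor and the medical advisor. The cost is a protocol wording change, with no effect on sample size or data collection.
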